9.3. Participant pathway summary

Participants will be invited to take part by either [name] or by a primary care practitioner in their General Practice clinics. Participants will provide informed consent after they have read the study information sheets and have time consider their involvement (minimum 24 hours) and ask any questions.

Upon providing informed consent the participants will visit QMUL laboratories for a screening assessment. During this one hour visit they will complete a submaximal exercise test on a static bike (to provide estimates of maximal exercise capacity to standardise exercise exposure protocol) and perform pre and post bronchodilator

spirometry and exhaled nitric oxide testing and oscillometry. At this point participants will be sent an online link to the symptom surveys. Surveys will be explained to the participants and they will be asked to complete the surveys they days before the testing visits. Participants will be provided with personal air quality monitor, heart rate monitor and physical activity monitor to wear three days before the exposure visit.

Participants will be invited to visit one of three field based study sites in a random order. Study sites will be located in walled gazebos next to air quality monitoring sites (managed by our collaborators at ICL) positioned near roads to provide the required air quality exposure. The protocol for the three visits will be identical and each visit will be separated by at least two weeks (washout). Participants will initially provide a urine sample at home and will bring the sample with them to the testing site. To control for participant exposures before testing, a taxi will be provided for the participant. Participants will travel with car windows closed, and air recirculation turned on. Participants will arrive that the study site at 10:00am, and will be joined by up to three other participants. In the first hour the participants will perform the respiratory health assessments and will provide a blood and a nasal mucus sample. After performing all the pre exercise tests participants will wear a heart rate monitor and will commence the exercise protocol (six exercise bouts of 15 minutes separated by fifteen-minute rest periods on a static exercise bike). Half-way through the protocol participants will perform spirometry, impulse oscillometry and FeNO testing. Upon completing the two-hour exercise protocol participants will complete the same battery of health assessments and will provide nasal mucus samples. Participants will leave the assessment area at about 14:00pm. Air pollution measurements will be taken for the duration of the time that the participant visits the exercise location.

24 hours after the exercise protocol participants will visit the QMUL laboratories to perform the health assessment tests again and to provide a mucus sample via nasal lavage, blood sample via venepuncture and provide a urine sample. After repeating this process three times (one visit to each field site) they will receive an expenses payment of £200 and leave the study. Participants will be paid £60 per exposure visit and £20 pre-screening visit. Participants will be paid for each visit they attend and will be paid when they complete participation or withdraw from the study.

9.4. Exposure site selection:

The two air quality supersites in London, located in a suburban park in South London (Honor Oak Park) and close to a major trunk road in Central London (Marylebone Road), will be used as a basis for this study. These are owned and managed by ICL and provide the required facilities and the highly time resolved chemical composition measurements required to quantify the non- tailpipe component of PM. An additional measurement location will be established at ICL's White City campus for the duration of the study using ICL's mobile measurement facility,¹³ equipped with the same highly time resolved chemical composition measurement capability as the supersites. This location provides the contrast in non-tailpipe contributions being next to the high

speed A40 flyover and the required facilities to support the trial which are not available at other LAQN measurement locations.

Figure 1: Air quality supersites: Marylebone Road (left), Honor Oak Park (centre), mobile measurement station (right)

The Marylebone Road station is located 2m from kerbside, this major trunk road carries 51,000 vehicles per day - 4% Heavy goods vehicles (HGV), 3% Buses, 16% light goods vehicles (LGV);¹⁴ average speed is 34 kph (21 mph). The stop-go traffic on this congested road increases brake wear relative to tire wear and resuspension. This is confirmed by the LAEI, which estimates 51% of NTE as brake wear compared to 39% as resuspension and 10% as tyre wear. There is a large area of sidewalk next to the cabin that will be segregated from the public for the exercise compound and public toilets are less than 100m away, equipment will be stored in the station between exposures.

The proposed location on ICL's White City campus is 5 m from the kerbside of the busy A40 flyover, carrying 93,000 vehicles per day - 6% HGVs, 17% LGVs;¹⁴ average speed was 33-59 kph (21-37mph). This road is a major route into and out of Central London, the high number of HGV and associated vehicle weight will lead to increased resuspension and tire wear.^{15,16} Due to the higher speeds and more free flowing traffic, the LAEI estimates this location to have only 85% of the brake wear emissions of the Marylebone Road measurement location thereby increasing the contrast between the two traffic locations. There is ample room on the campus to segregate as an exercise compound and the adjacent Michael Uren Engineering Hub will provide equipment storage and toilet facilities.

9.5. Air Pollution Measurements and Characterization of Non-Tailpipe Emissions:

The air quality monitoring stations will provide, measurement data according to the data quality assurance procedures described below, they will also enable a robust determination of the sources of tailpipe, non-tailpipe and other urban and regional sources of PM₁₀ and PM_{2.5}.

Table 1: Air quantity station measurement configuration

Measurement	Stop-go traffic	High speed continuous traffic	Urban background
	Marylebone Road	White City	Honor Oak Park
PM ₁₀ and PM _{2.5}	Optical Particle Counter, Fidas 200E, Palas, DE		
NO ₂	T200 Chemiluminescence NO/ NO _x , Teledyne, USA		T500U Cavity Attenuated Phase Shift (CAPS), Teledyne, USA
NO, NO _x or NO _y			T200U Chemiluminescence NO/ NO _y , Teledyne, USA
O ₃	T400, UV Absorption O ₃ Analyzer, Teledyne, USA		
37 elements (Al, Si, P, S, Cl, K, Ca, Sc, Ti, V, Cr, Mn, Fe, Co, Ni, Cu, Zn, Ga, Ge, As, Se, Br, Rb, Sr, Y, Zr, Nb, Cd, In, Sn, Sb, I, Ba, Hg, Tl, Pb, Bi)	Xact Multi-Metals Monitoring System, Cooper Environmental Services, USA		
Organic Mass, NO ₃ , SO ₄ , NH ₄	Aerosol Chemical Speciation Monitor (ACSM), Aerodyne Research Inc, USA		
Black Carbon	Aethalometer AE33, Magee Scientific, USA		

The measurement stations are all part of the London Air Quality Network (www.londonair.org) and or the UK government's Automatic Urban and Rural Network (<https://uk-air.defra.gov.uk/networks/network-info?view=aurn>)

- PM₁₀ and PM_{2.5} is measured using the Fidas 200E which is certified for use on UK air quality networks and have demonstrated equivalence to the reference

method through extensive laboratory and field tests in the UK and EU (<https://uk-air.defra.gov.uk/networks/monitoring-methods?view=mcerts-scheme>).

- Oxides of nitrogen (NO, NOX, NO₂) is measured using ozone chemiluminescent; this is the standard approach for monitoring networks in the UK and internationally.
- The urban background station is more focused on atmospheric research and is therefore equipped with more highly specified measurement equipment; it measures NO₂ using Cavity Attenuated Phase Shift (CAPS) and NOY rather than NOX to minimize sample loss in this lower concentration environment.
- O₃ is measured at all stations using UV Adsorption.

The air quality supersites stations at Honor Oak Park and Marylebone Road are equipped with high time resolution chemical composition measurement techniques and particle counters as part of the UK's Government's Particle Numbers and Concentrations Network or through funding from UK Research and Innovation funding and are managed and operated by Imperial College London

The Xact Multi-Metals Monitoring System (Cooper Environmental, USA) measures 37 elements between Al and Bi at an hourly time resolution using ED-XRF (Tremper et al., 2018). To maximise size and chemical composition information, PM_{2.5} and PM₁₀ are collected onto the Teflon filter tape on alternate hours using a switching valve and intermediate hours are interpolated as described by (Manousakas et al., 2022).

The ACSM (Aerodyne Research Inc, USA) is a widely research instrument (Ng et al., 2011) and is extensively being used in advanced measurement networks around the world to measure the non-refractory composition of aerosols.(Bressi et al., 2021) All ACSMs used in this study utilize a quadrupole mass spectrometer, the Honor Oak Park instrument uses a PM_{2.5} lens(Joo et al., 2021) while the roadside instruments use a PM₁ lens to minimize lens transmission losses of freshly emitted aerosols close to vehicles(Xu et al., 2017).

The AE33 Aethalometer measures the attenuation of light transmitted through the sample collected on a filter, which is then converted to a black carbon measurement.

The road surface conditions will be collected from surface sensors at Marylebone Road (DRS511, Vaisala, Finland) and using a camera at White City Flyover (DSC111, Vaisala, Finland), this will be used to differentiate wet and dry road surface conditions a per Hicks et al 2021(Hicks et al., 2021).

9.5.2 Source Apportionment

The equipment discussed will identify sources of NTE by quantifying and source apportioning the high time resolution chemical composition measurements described above to produce time series and factor profiles of source emissions in organic aerosols and elemental compositions.

Using high time resolution data in this way addresses many of the challenges faced when quantifying the different sources in the urban environment as the higher time resolution yields a greater variability from changing emission characteristics, boundary layer dynamics, and reflects short lived events which are obscured by the long sampling time of filter-based approaches (Wang et al., 2018). This variability is fundamental to improving the performance of multivariate statistical approaches which are used to estimate the source contributions and fingerprints to solve a mass balance. Positive Matrix Factorization (PMF) (Paatero and Tapper, 1994) is the most commonly used of these and the solutions describe the complex, time-dependent aerosol composition as a linear combination of factor profiles and their contributions. It has been used extensively for the identification of heavy metals, water soluble and carbonaceous sources (Hopke et al., 2020) and for high-time resolution elemental data from the Xact (Font et al., 2022b, Hasheminassab et al., 2020, Liu et al., 2019, Rai et al., 2020, Rai et al., 2021, Wang et al., 2018, Yu et al., 2019, Manousakas et al., 2022).

PMF will be applied to the PM₁₀ and PM_{2.5} Xact data and ACSM data from all 3 stations using the Source Finder software (SoFi Pro, <https://datalystica.com/>), which has been used by the ICL team in numerous studies (Font et al., 2022b, Fröhlich et al., 2015, Manousakas et al., 2022, Reyes-Villegas et al., 2016, Visser et al., 2015b) to provide hourly source factor time series and factor profiles for the duration of the exposures. For the ACSM data, the Sofi software has been used in many recent advances to reduce the uncertainty associated with rotational ambiguity by introducing a priori information about the source profiles (Canonaco et al., 2013, Canonaco et al., 2021) and is now widely used in that community. (Crippa et al., 2014) Recent work on data from Zurich (Manousakas et al., 2022) has shown that source apportionment of the XACT PM₁₀ and PM_{2.5} data can be used to quantify the emissions from a range of sources in urban background locations.

Separating the tire and road wear sources is not straight forward as they are internally mixed and generated by the same frictional forces. To help understand some of these processes in greater depth, additional size fractionated measurements of polymers are planned at Honor Oak Park and Marylebone Road during 2022/23 under a separate project (NERC, 'Understanding UK airborne microplastic pollution: sources, pathways and fate').

9.6. Pre-assessment screening

Following provision of written informed consent, study volunteers will undergo pre-assessment screening at QMUL. They will complete baseline FeNO and spirometry, pre- and post-bronchodilator, to confirm asthma status (based on FEV₁ reversibility and patient interview). A blood sample (10ml in single draw) will be collected to assess a full blood count including eosinophil levels, and specific immunoglobulin E (IgE) levels across a panel of common aero-allergens (to be included as a study confounding variable). Participants will then perform a submaximal cycle ergometer exercise test (Latin Protocol) to establish the exercise watt levels to be used at the site visits. If they wish participants can warm up by walking on a treadmill prior to the exercise test. Participants will be given a personal air quality monitor to wear for three days before the exposure visit.

9.7. Randomization

The study will use a 6X3 Williams crossover inequality test of paired differences.¹⁷ as such the participants will be randomised to a sequence for their exposures to the three sites. Six sequences will be used (ABC/ BCA/ CBA/ ACB/ BAC/ CAB).

9.8. Health effects assessment on exposure visit days:

Participant flow through an exposure session is summarised in figure 2, while participant flow through the study is summarised in figure 3. On the morning of the site visits participants will first provide a urine sample while at home (9:00 am) Participants will be provided with a taxi to the study site. The participants will be transported taxi with closed windows and air circulation enabled, to the exposure sites.

Once at the exposure sites (10:00am-11:00am) baseline spirometry and determination of FeNO and sample collection (4x10 ml blood collection and baseline nasal lavage) will be performed at the field laboratory. At this time a brief health questionnaire will be administered to assess recent asthma control and ensure the volunteer is free of respiratory infection and has not experienced a recent exacerbation of their asthma.

During the two and a half hour exposure and exercise protocol (11:00am-13:30 pm), participants' heart rate will be monitored throughout the exposure period; at the half way point, after sufficient recovery (12:15am) participants will perform spirometry FeNO and Oscillometry. Immediately post-exposure the participants will perform spirometry, oscillometry FeNO and mucus sample collection at the field lab. The following day, volunteers will return for 28-hour post measurements; biosamples, spirometry and FeNO.

IONA: Schedule of assessment and exposure								
	Pre-Study	Screening	3 day pre	Pre	Exposure	Post	24 hour post	3 days post
		Phys lab	Self assess	Field lab	Field lab	Field lab	Phys lab	Self assess
Consent	x							
Exercise test		x						
FeNO		x		x	x	x	x	
Oscillometry		x		x	x	x	x	
Spirometry		x		x	x	x	x	
Asthma control test		x						
QOL: AQLQ		x						
Baseline questionnaire		x						
Daily Symptom Q		x	x	x		x	x	x
PEF Test			x				x	
Personal air quality			x					
Physical activity			x					
Venepuncture				x			x	
Nasal lavage				x		x	x	
Urine sample				x			x	
Heart rate					x			

Figure 2. Flow of participants through IONA study days

Our primary endpoint, lung function (FEV1) will be assessed using a portable desktop computerized spirometer (Vitalograph). All procedures will be performed in accordance with American Thoracic Society guidelines. Predicted volumes will be calculated according to the global lung index guidelines to adjust for ethnicity.²⁰ As Forced Expiratory Flow (FEF)₂₅₋₇₅ is a volume dependent measurement, decreases in forced vital capacity (FVC) following exposure to air pollutants affect this parameter. It has been demonstrated however that isovolume adjustments to this parameter provide a useful means of accessing intrinsic narrowing of the peripheral airways.²¹ We therefore propose to correct the measured flows to the participants predicted total lung capacity, using the forced expiratory flow at 50 and 60% of predicted total lung capacity (TLC): FEF_{50%TLC} and FEF_{60%TLC} respectively.²² The area under the forced expiratory flow curve will also be determined, as this has been suggested to be a sensitive indicator of bronchoconstriction. Fractional Expired Nitric Oxide and impulse oscillometry and asthma symptoms will also be collected before, during and after the exposure tasks in accordance with European Respiratory Society guidelines.

[figure not shown]

Figure 3. Flow of participants through IONA.

9.9. Abstaining from medication.

Participants will continue to use all their routine asthma medication during the study. In agreement with ERS spirometry guidance participants will be asked to abstain from using reliever medication for six hours prior to performing spirometry. If participants need to use their medication in the six hours prior to the first spirometry testing of an assessment visit they will be offered an opportunity to reschedule the assessment visit. If participants need to use their inhaler during the testing protocol the testing will end immediately. If a participant wishes to continue with the study, they will be offered another testing date, after a brief discussion with [name] (GP specialising in Asthma). If testing is stopped after discussion with [name] participants will still receive all expenses, and this will be made clear to the participants at the start of the study.

9.10. Exercise and exposure protocol:

To control for variations in air quality, exposure will occur for two-and-a-half hours between 11:00am and 13:30pm on weekdays. Between pre- and post- health assessments, participants will be asked to cycle on a static exercise bike at a watt equivalent to 60% of estimated heart rate maximum for six exercise bouts of 15 minutes separated by fifteen minute rest periods. This exercise intensity was chosen to maximise inhaled doses of PM and gaseous pollutants over the exposure period while remaining below the first ventilation threshold to reduce variation in ventilatory drift, and minimising discomfort for the participants. Physiological drift will be monitored by Ratings of Perceived Exertion questionnaire and real-time monitoring of the participants heart rate and estimated breathing rate.

9.11. Participant withdrawal

[figure not shown]
Participants will be informed and reminded that they can withdraw from the study at any time. Participants will be able to choose to start cease their involvement with the study or to cease their involvement and have their data removed from the study.

Consent forms and information sheets will tell participants their last time opportunity to have their data removed from the study.

9.12. End of study definition

The end of this study is defined as the date on which the last data is collected.

9.13. Study Timeline

10. Statistical considerations

10.1. Sample size

Since we will randomize the participants to assign a sequence for their exposures to the three sites we will have six sequences (ABC/ BCA/ CBA/ ACB/ BAC/ CAB), a 6X3 Williams crossover inequality test of paired differences.¹⁷ For a significance level of 0.05, a Δ (Difference between the reduction in FEV1 between 2 sites) of 4.69 with a standard deviation of 6.4²³ and a total of 30 participants (5 per sequence) we have a power of 91.54%. However, assuming a dropout rate of 20 to 30% and taking into account that specific exposures to contrast are not available yet and will be assessed when the exposure methods are developed, we intend to recruit 48 participants in total. We will define 12 groups of 4 individuals and then assign a group to each participants. Each two groups will have a same sequence.

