Inclusion and exclusion criteria	
Inclusion criteria:
 
 • Doctor diagnosed asthma starting on or before age 16 years • Prescribed regular inhaled corticosteroid medication • Able to use a static exercise bicycle for the study duration 
Exclusion criteria:
 
 • Tobacco smoking, or living with smoker • Body mass index (BMI) > 30 • Asthma hospitalisation within 12 months • Three or more asthma episodes requiring oral corticosteroid medication within 12 months • Other major lung disease • Chest surgery within 6 months • Unable to give informed consent • Occupational exposure to particulate matter (PM) or high levels of air pollution
Statistical methodology and analysis (if applicable)	Mixed effects models, taking into account repeated measurements within participants.
Study duration	01/08/2022- 1/12/2024

5. Introduction

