10.3. Statistical modelling

We will use mixed effect regression model to estimate the effects of different pollutant sources (tailpipe or non-tailpipe) on the change in health point, which will be defined by difference of various factors such as FEV1 and FVC between pre-exposure and post-exposure (0, 2, or 18 hours). For each endpoint, one key time post-exposure has been selected, based on the time of maximal effect in previous controlled exposure studies, for example for FEV1 this is 2 hours post exposure.²³ In this model, when measurements and pollutant characterization become available, the exposure covariates will be the integrated average concentration of the various pollutants and /or sources during the exposure period. We will take the results of the source apportionment and feed them into the model. The method will provide estimates of exposure due to tailpipe emissions (Black Carbon and Organic Aerosol) and non-tailpipe, specifically break wear and tyre & road wear, emissions. We will include these exposure types in the model. We will start with a single-exposure covariate models (for every source type), then we can decide how to develop a model with all of the significant source types. Levels (eg. Integrated average concentration) of each source (tailpipe/non-tailpipe) will be included in the model. The effects of different pollutants will be compared based upon statistical significance and the effect size for selected exposure contrasts, such as a pre-defined change of the concentration of the pollutant or interquartile range. Two pollutant models will be specified as well to evaluate which pollutant has the strongest association with a certain health endpoint.

In our models we will account for potential confounders which may be present as the exposure contrast cannot be entirely predicted by the design: we will include meteorological variables such as temperature, relative humidity and wind direction during the exposure time; as well as individual characteristics such as age, gender, severity of asthma and allergies.

We will use R (version 4.1.3 or newer; R Development Core team) for the application of mixed models using functions from the lme4 and nlme packages.

11. Ethics

The study will be sponsored and managed by QMUL and supported by Imperial College London, according to MRC guidance:

<https://www.mrc.ac.uk/publications/browse/good-research-practice-principles-and-guidelines/>

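### Up to four participants share an exposure session, but the only dependence the protocol names is within participant; section 10.3 should add a session term.

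*Protocol*

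**What the plan says.** Protocol section 10.1 sets up the allocation: "We will define 12 groups of 4 individuals and then assign a group to each participants". It adds: "Each two groups will have a same sequence". That makes 12 groups over six sequences, two groups to each.

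Section 9.3 describes a visit: "Participants will arrive that the study site at 10:00am, and will be joined by up to three other participants". A session therefore holds at most four people, the same number as a group. Section 9.9 lets individual visits move. If a participant has needed reliever medication shortly before testing, "they will be offered an opportunity to reschedule the assessment visit".

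Section 10.3 states the analysis: "We will use mixed effect regression model to estimate the effects of different pollutant sources (tailpipe or non-tailpipe) on the change in health point". In that model "the exposure covariates will be the integrated average concentration of the various pollutants and /or sources during the exposure period". For confounding, "we will include meteorological variables such as temperature, relative humidity and wind direction during the exposure time".

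The statement about dependence is in the synopsis (section 4): "Mixed effects models, taking into account repeated measurements within participants". No session, date or group effect is named anywhere. Sections 9.7 and 10.1 name a Williams paired-difference comparison between sites, and 10.1 powers it with 30 participants treated as independent.

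**The concern.** People tested together share the site, date, air, weather, staff and instruments. Their FEV1 changes may move together for reasons that a participant effect cannot capture. The station-measured exposure also has one value per session, so the people in a session are not separate replicates of that exposure. If groups of four attend together, 48 × 3 = 144 participant-visits come from only 12 × 3 = 36 site-days.

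A model with a participant effect alone treats those people as independent once their own repeats are accounted for. Any shared variation left over makes the reported standard errors too small and false positives too frequent. This touches the site comparison in the primary objective and the source effects that carry the study hypothesis.

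**Working it through.** **Inputs.** From section 10.1: difference 4.69, SD 6.4, 30 participants for power, stated power 91.54%, 48 recruited, dropout 20 to 30%, 12 groups. From section 9.3: up to four per session. Assumed, because the protocol does not give it: within-session correlation ρ of 0.05 to 0.3, meaning what remains after change scores and covariates.

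**Step 1: the plan's own figure.** The noncentrality is 4.69/6.4 × √30 = 4.014. With 6 × (5 − 1) = 24 df, two-sided power is 91.54% at 0.05/3 and 97.1% at an unsplit 0.05. The stated figure is thus reproduced exactly at 0.05/3. It makes no allowance for shared sessions.

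**Step 2: completers per group.** 48 × 0.7 = 33.6, about 34. 48 × 0.8 = 38.4, about 38. Mean group size m is 34/12 = 2.83 or 38/12 = 3.17.

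**Step 3: standard error and power if groups attend together.** If each session contributes a share ρ of the residual variance, two members of a group have paired site differences correlated at ρ. The design effect is then DEFF = 1 + (m − 1)ρ, and the true standard error is √DEFF times the reported one. For example, at m = 3.17 and ρ = 0.3, DEFF = 1 + 2.17 × 0.3 = 1.65 and √1.65 = 1.285. An approximate type I error for a nominal 5% test is 2Φ(−1.96/√DEFF). Power at 0.05/3 uses noncentrality 4.69/6.4 × √(N/DEFF) with N − 6 df.

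| N | ρ | SE increase | Type I error, formula | Type I error, simulated (site contrast) | Power at 0.05/3 |
|---|---|---|---|---|---|
| 34 | 0.05 | 4.5% | 6.1% | 6.1% | 93.1% |
| 34 | 0.1 | 8.8% | 7.2% | 7.5% | 90.8% |
| 34 | 0.2 | 16.9% | 9.4% | 10.3% | 85.8% |
| 34 | 0.3 | 24.5% | 11.5% | 13.6% | 80.5% |
| 38 | 0.05 | 5.3% | 6.3% | 5.7% | 95.6% |
| 38 | 0.1 | 10.3% | 7.6% | 7.7% | 93.5% |
| 38 | 0.2 | 19.7% | 10.2% | 9.7% | 88.6% |
| 38 | 0.3 | 28.5% | 12.7% | 14.9% | 83.2% |

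The simulation used 2,500 trials per row. Completers were drawn at random from 12 groups of four, so group sizes were unequal. The fitted model had site, period and participant effects only. The Monte Carlo standard error in the last row is √(0.149 × 0.851/2500) = 0.7 percentage points, and a repeat with 10,000 trials gave 14.4%.

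With session-level df (36 sessions − 12 groups − 2 site − 2 period = 20), the lowest power is 78.5%, at N = 34 and ρ = 0.3.

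**Step 4: source effects.** With a session-level exposure and three session-level weather covariates, type I error with participant effects only was 6.6, 7.6, 11.3 and 14.9% (N = 34) and 6.8, 8.4, 10.7 and 13.9% (N = 38) over the same four values of ρ.

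**Step 5: individual rescheduling.** With a quarter of visits moved to sessions of their own, the site contrast gave 5.9, 6.2, 7.5 and 9.4% (N = 34) and 5.8, 6.3, 7.6 and 9.9% (N = 38).

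**Step 6: with a session intercept.** Fitted by REML with Satterthwaite df, type I error was 3.5 to 5.3% for the site contrast and 3.8 to 6.7% for the source effect. Power at 0.05/3 was 77 to 94%.

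**The case against.** The strongest reply is that random-effect structure and df methods are usually left to an analysis plan, which is not at hand. The synopsis line is a one-line summary that does not say participant is the only random term, and a mixed model can hold a session term. That stands to this extent: the protocol is silent on sessions and does not rule the term out. But it fixes the grouping, the shared sessions and the session-average exposure itself. A reader who follows its text would fit participant alone.

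Second, nothing says that the 12 groups attend together. The allocation sentence assigns a group to each participant, which may only be a way to balance sequences. Four is a cap on session size, and section 9.9 lets visits move. This stands, so 36 site-days is the limiting case and not an established count.

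Third, ρ is assumed, and change scores, measured pollutants and weather remove part of the shared variation. This also stands. At ρ = 0.05 the error rate is only about 6%, and rates above 10% need joint attendance and ρ of roughly 0.2 or more.

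Fourth, objective 3 and section 14.3 also use nasal deposited dose, which is measured in each participant. The argument that exposure varies only between sessions does not cover that analysis.

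A reader might also infer three stronger points, which the protocol does not support:

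- **That the trial is underpowered.** Recruiting 48 leaves room, as the working shows.
- **That 91.54% is wrong.** It is reproduced exactly and is conservative against an unsplit 0.05.
- **That the site comparison is missing.** Sections 9.7 and 10.1 name it. Section 10.3 does not repeat it, which is a matter of placement.

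**Conclusion.** The concern holds in a limited form. The protocol puts up to four people in one session and uses session-average exposures, but names dependence only within participants. If residual session correlation exists, site contrasts and station-measured source effects will be reported with too much precision. Under joint attendance, ρ of 0.05 to 0.3 and 34 to 38 completers, the standard error is understated so that the true one is about 4 to 29% larger, and type I error for the site contrast is about 6 to 14%. Individual rescheduling lowers this, and participant-level exposures such as nasal dose are less affected. Both ρ and joint attendance are assumptions. The issue is type I error and not sample size. The session term is a cheap improvement, best written in before analysis.

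**What to change.** In section 10.3, add a random intercept for the exposure session actually attended (site by date) beside the participant effect, with Satterthwaite or Kenward-Roger df. Apply it in the source models that use station-measured exposure and in the site comparison named in 9.7 and 10.1. Defining the term by actual attendance means it works whether or not groups stay together. It also lets the data estimate the correlation.

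Two clarifications go with it. Cross-refer the site comparison in 10.3. In 10.1, note that 91.54% corresponds to 0.05/3 per contrast with 24 df, if that was intended.

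The cost is one random term, a df method and a few sentences. Intervals become slightly wider, and at small ρ the site test is somewhat conservative (3.5 to 3.8% at ρ = 0.05). If there is no session correlation at all, simulated power at 0.05/3 falls from 96.3 to 92.0% with 34 completers and from 97.6 to 95.1% with 38. No extra participants are needed.
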